“Improving Glycemic Control in DM2 Patients in the Ambulatory Setting”

PI [name]
NCT04800471

COVER PAGE

“improving Glycemic Control in DM2 Patients in the Ambulatory Setting”

Introduction

PI: [name]

NCT 04800471

Date: 02/26/2021

“Improving Glycemic Control in DM2 Patients in the Ambulatory Setting”

PI [name]
NCT04800471

“improving Glycemic Control in DM2 Patients in the Ambulatory Setting”

Introduction

Managing patients with type 2 diabetes mellitus (T2DM) bears considerable challenges, as precise glucose monitoring and adherence to insulin therapy are necessary to guide therapeutic interventions. Although novel technological solutions such as automated insulin closed-loop delivery systems are available, many patients are treated with multiple daily insulin (MDI) regimens and use point-of-care (POC) fingerstick testing for glucose monitoring. POC testing is a relatively painful method with multiple limitations, including insufficient glucose information, lack of compliance, and potential errors (e.g., handwritten logs). In addition, obtaining accurate information on insulin administration is hindered by the prevalent use of traditional insulin pens. Consequently, when making treatment decisions, healthcare professionals (HPC) often rely on self-reported glucose values and the assumption that patients adhere to treatment plans. Unfortunately, insulin adherence among patients with T2DM is problematic, and many patients have poor compliance with insulin therapy.

Recent advancements in diabetes technology offer patients and HCPs efficient and reliable alternatives for obtaining glucose metrics and monitoring compliance. Continuous Glucose Monitoring (CGM) devices provide a sophisticated method of tracking glucose levels, gathering

“Improving Glycemic Control in DM2 Patients in the Ambulatory Setting”

PI [name]
NCT04800471

high volumes of data continuously and automatically at frequent intervals. Additionally, Smart Insulin Pens (SIPs) record the timing and dosage of insulin, therefore documenting adherence. Utilizing software applications, data recorded by CGM and SIPs can then be shared with clinicians through Bluetooth and Internet connectivity.

Lifestyle intervention is also an essential component of diabetes treatment and managing patients with T2DM successfully involves promoting physical activity (PA). Increasing PA is associated with improved glycemic control, decreased risk of cardiovascular disease, and lower mortality. Despite its importance, most patients with T2DM remain physically inactive.

Optimizing glycemic control requires, however, frequent outpatient clinic visits for medication adjustments. Given that over 38 million Americans live with diabetes and approximately 90-95% of them have T2DM, managing such a high volume can be challenging through traditional face-to-face clinic visits. Additionally, many patients with T2DM have underlying comorbidities that restrict mobility or live in remote areas, posing barriers to seeking in-person care. Telemedicine can serve as an alternative method of providing less time-consuming and more accessible patient care, allowing quicker titration of DM medications and improving monitoring and compliance in medication taking. However, most patients continue to be seen through face-to-face visits, and previously described telemedicine systems are limited by POC testing and traditional insulin pens.

“Improving Glycemic Control in DM2 Patients in the Ambulatory Setting”

PI [name]
NCT04800471

With this study, we will perform a pilot randomized control trial (RCT) to examine the effectiveness and feasibility of a novel integrative telemedicine system for patients with T2DM, which combines CGMs, SIPs, official consultation from an exercise physiologist to promote PA and use of telecommunication methods.

Description of the Integrated Telemedicine Model

Our integrated telemedicine system is described below. First, to obtain glucose/insulin data, we will use a) CGM devices (Dexcom G6) and b) SIPs (Medtronic InPens for short-acting insulin and Insulclock Caps for long-acting insulin. Insulclock data will only be used for recording compliance and not for treatment decisions). Using Bluetooth technology and software applications, glucose, and insulin data from CGMs and SIPs will be sent to patients' smartphones, allowing them to make the recommended treatment decisions (e.g., prevent hypoglycemia, extra-correction insulin for hyperglycemia treatment, among others). Next, using program applications (i.e., Dexcom Clarity, Medtronic InPen), CGM/SIP reports will be generated to provide information relating to insulin nonadherence and patterns of hypo-hyperglycemia. Finally, HCPs will review the generated reports through commercial internet or Wi-Fi and use telecommunication systems (i.e., VA Video Connect (VVC), secure messaging (SM), or telephone call) to communicate with the patients and provide treatment recommendations. Additionally, during these telemedicine visits, an exercise physiologist (EP) will meet with participants remotely every three months. At the first EP appointment, a personalized and evidence-based PA prescription will be developed using information provided by the subjects to carry out the prescription (e.g., tips for making time to stay active and referral to technical instruction videos). In subsequent follow-up telemedicine visits, EP

“Improving Glycemic Control in DM2 Patients in the Ambulatory Setting”

PI [name]
NCT04800471

provider will give personalized feedback on successes and challenges with performing PA and T2D behavioral skills.

Patient Population-Study Procedures

In this prospective, randomized control pilot study will be conducted at the Baltimore VA Medical Center (BVAMC), 30 patients with T2DM will be enrolled. Subjects who met at least one inclusion and none of the exclusion criteria defined below they will participate after they signed an informed consent.

Inclusion Criteria:

Insulin-treated patients with DM2 (treated with basal-bolus insulin regimens (MDI), \pm non-insulin medications) and Uncontrolled glycemic control

Exclusion Criteria:

- History of type 1 DM (DM1)
- Pregnant Patients
- Extensive skin changes/disease or allergies that preclude wearing the CGM sensor
- Subjects who have end-stage renal disease requiring dialysis
- Significant psychiatric illness or any other condition rendering the subject incapable of understanding the objectives and potential consequences of the study

Participants will be randomly assigned using a computer-generated random sequence at a 1:1 ratio to either the Telemedicine group or the Standard of Care (SoC) group. All participants will be followed for six months, unless they died or if they withdrew consent and decided not to

“Improving Glycemic Control in DM2 Patients in the Ambulatory Setting”

PI [name]
NCT04800471

continue participating in the study. No sample size calculations are provided due to the pilot nature of this study. Instead, we used a convenience sample of 30 subjects. This study was approved by the BVAMC IRB Committee.

Following consent, subjects in both groups will have a baseline research visit where they will be placed on a ("blinded") Dexcom G6 CGM device for ten days to obtain baseline CGM glucose data. A baseline assessment of PA will be obtained by completion of the Senior Fitness test. Subjects will be then randomized to either Telemedicine or the Standard of Care (SoC).

Participants in the telemedicine group will be educated about the appropriate use of the telemedicine system components. They will be asked to use their CGMs for ongoing automatic glucose monitoring, SIPs for insulin administration with recording insulin use, software applications, and VVC, SM, and telephone for telemedicine visits. Participants in the SoC will receive diabetes education as per standard of care (i.e., frequency of POC checking and proper insulin administration, among others). They will be asked to use POC for glucose monitoring and traditional insulin pens for insulin administration, and they will be asked to document POC, and insulin use as per standard of care.

Then, following the initial baseline visit, patients in the Telemedicine group will have the following interventions:

- i) in-person (Initial) Clinic Visit (Day 0):*

“Improving Glycemic Control in DM2 Patients in the Ambulatory Setting”

PI [name]
NCT04800471

This will be a typical in-person clinic visit. Vital signs, medications, and a medical history will be obtained. POC values will be reviewed, and DM medication adjustments will be performed. CBC, BMP, HbA1c, and urine creatinine/microalbumin will be obtained per usual care.

ii) Telemedicine visits (~every three weeks until +180 days [end of RCT]):

Approximately every three weeks, patients will have remote visits using the DAT clinic. HCPs obtained CGM and SIP data using software applications (as above). Trends of hyperglycemia and hypoglycemia and their relationship with insulin administration will be identified, leading to adjustments of diabetes medications (insulin or non-insulin). Communication will be done by VVC, SM, or by phone. Patients will be evaluated more (i.e., if acute changes are needed after hypoglycemic events) or less frequently (i.e. if no changes on medications are needed). At the last remote visit (+180 days), all patients will have repeat lab work of CBC, BMP, HbA1c, and urine creatinine/ microalbumin.

iii) Consultation (telecommunication) by an exercise physiologist (Days 0, +90 days, +180 days [end of RCT]):

On day 0, the exercise physiologist will evaluate baseline PA data and medical history, telecommunicate with each participant regarding their PA goals, facilitators, and barriers, and will write a PA prescription (frequency/intensity/duration/type) following best practices 64. On days +90 and +180, he will discuss progress, set motivational intermediate goals to reach the long-term PA prescription objectives, and will modify exercises as needed.

"Improving Glycemic Control in DM2 Patients in the Ambulatory Setting"

PI [name]
NCT04800471

iv) Research Visit: At +180 days (end of RCT):

Subjects will be placed on a "blinded" CGM. After ten days, Veterans will be asked to return the CGM, which will be downloaded. Subjects will complete the Senior Fitness test for PA evaluation.

Following the initial baseline visit, subjects in the SoC group will have the following interventions:

i) One in-person (Initial) Clinic Visit (Day 0):

This visit will be identical to the in-person visit that subjects will be randomized to the Telemedicine group had on Day 0.

ii) Two in-person Clinic Visits (Day +90, +180):

Subjects will have a typical clinic in-person visit. Vital signs and HbA1c will be obtained, physical examinations will be performed, and POC values (either by report, logbook, or glucometer) will be reviewed. Information regarding insulin use and adherence will be obtained through patient reporting. DM medication adjustments will be performed, and patients will be instructed to increase their PA as clinically indicated.

iii) One Research Visit: This visit will be at +180 days (end of RCT) and will be identical to the research visit of the Telemedicine clinic group.

“Improving Glycemic Control in DM2 Patients in the Ambulatory Setting”

PI [name]
NCT04800471

Outcome Measures

The purpose of this trial will be to examine the feasibility of the above interventions (CGMs, SIPs, Telecommunication systems and promoting PA by EP) combined as a single telemedicine intervention and examine whether it can lead to improvement in hyperglycemia, as defined by a decrease in HbA1c (primary outcome). Secondary outcomes will be time in range (TIR) 70-180 mg/dL, time below range (TBR) <70 mg/dL, TBR <54 mg/dL, time above range (TAR \geq 180 mg/dL and TAR \geq 250 mg/dL. In addition, we will evaluate differences in hypoglycemic events (CGM glucose <70 mg/dL for at least 15 minutes), clinically significant hypoglycemic episodes (CGM glucose < 54 mg/dL for at least 15 minutes), and nocturnal hypoglycemia. For glucose variability, we will evaluate if there is a difference in the Coefficient of Variation (CV).

STATISTICAL ANALYSIS

Student's t-test will be used to compare baseline characteristics of the two groups. For continuous outcome measures (e.g., HbA1c, time <54 mg/dL, etc.), we will use linear regression analyses (SAS proc genmod with a normal distribution and identity link). For outcome measures that will be counts (e.g., number of hypoglycemic episodes <54 mg/dL), we will use Poisson regression (SAS proc genmod with a Poisson distribution and a log link). Regardless of the type of regression we will use, the model will be change in outcome= baseline value + group + time + group + time where group will be control or telemedicine and time will be baseline, three-month, or six-month. We will calculate estimated values at each time point using the mean value of the outcome at baseline, baseline value, (SAS LSMeans statement with a pdiff option). Comparisons of baseline

“Improving Glycemic Control in DM2 Patients in the Ambulatory Setting”

PI [name]
NCT04800471

characteristics will be performed using Student's t-test. A two-tailed $P \leq 0.05$ will indicate significance.

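### The follow-up blinded CGM is worn from +180 to about +190 days, so almost all of it falls after the stated end of the trial and after any change made at the +180 visits

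*Combined protocol and SAP*

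**What the plan says.** **Follow-up wear.** Item iv) of the Telemedicine schedule sets a research visit at +180 days, marked as the end of the RCT, at which a blinded CGM is placed. The next step is: "After ten days, Veterans will be asked to return the CGM, which will be downloaded". Item iii) of the SoC schedule sets an identical research visit on the same day. Patient Population-Study Procedures gives six months as the follow-up for all participants.

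**Other +180 contacts, Telemedicine.** Item ii) is headed "Telemedicine visits (~every three weeks until +180 days [end of RCT", and describes review of device data "leading to adjustments of diabetes medications (insulin or non-insulin". Item iii) schedules a consultation "by an exercise physiologist (Days 0, +90 days, +180 days [end of RCT". At +90 and +180 the physiologist reviews progress, sets goals "and will modify exercises as needed".

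**Other +180 contacts, SoC.** Item ii) places an in-person clinic visit at +90 and another at +180. At these visits diabetes medication is adjusted, and patients are told to be more active where appropriate.

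**Baseline wear.** Patient Population-Study Procedures describes a blinded "Dexcom G6 CGM device for ten days to obtain baseline CGM glucose data", then the fitness test, and then: "Subjects will be then randomized to either Telemedicine or the Standard of Care (SoC". The Day 0 clinic visit comes next in the text; there "POC values will be reviewed, and DM medication adjustments will be performed". No day number is given for the baseline visit.

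**Use of the data.** Outcome Measures lists the CGM outcomes as secondary or further outcomes. STATISTICAL ANALYSIS models change in each outcome, with the baseline value as a covariate. Neither section says which recording supplies the six-month CGM values.

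**The concern.** A six-month outcome should describe glucose during the six months of assigned management. This recording instead opens on the last day of that period and covers the ten days after it. That day is also a management day in both arms, so the values can include the early effect of changes made at the closing visits. They also cover a different stretch of time from the HbA1c obtained at +180.

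The wear also follows the last scheduled telemedicine contact. The protocol does not say whether telemedicine participants keep using their own CGM and smart pens, with clinician review, while the blinded sensor is on. A reader cannot tell which treatment condition the six-month CGM values represent.

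What is at stake is the meaning of the CGM results. The plan tests its outcomes at a two-tailed 0.05 level, and a pilot's CGM results are likely to inform any later trial.

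**Working it through.** The plan states no figure to reproduce. The check is timeline arithmetic, with inputs from the visit schedules cited above.

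**1. Current window**
- End of wear = placement day + wear length = 180 + 10 = about +190.
- Distance from the +180 visits and the stated end: 180 − 180 = 0 days to 190 − 180 = 10 days.
- The order of contacts within +180 is not stated. If they share a calendar day, at most about one wear day can precede a change made that day: 10 − 1 = about 9 of 10 days follow it, whichever contact comes first.

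**2. Does the window show a missed telemedicine contact?**
- Next visit at the nominal 21-day spacing: 180 + 21 = +201.
- Days 180 to 190 lie inside one nominal interval, so the timing alone shows no missed contact.

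**3. Window ending at +180**
- Placement = 180 − 10 = +170.
- SoC: 170 − 90 = 80 to 180 − 90 = 90 days after the +90 clinic visit.
- Telemedicine, counting forward from Day 0: 8 × 21 = +168, so 170 − 168 = 2 to 180 − 168 = 12 days after the previous nominal visit.
- Telemedicine, counting back from +180: 180 − 21 = +159, so 170 − 159 = 11 to 180 − 159 = 21 days.
- The telemedicine range is therefore 2 to 21 days. Actual visits may be more or less frequent, as the protocol allows.

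**4. Outcomes that depend on the wear**
- Secondary: TIR, TBR <70, TBR <54, TAR ≥180 and TAR ≥250 mg/dL = 5.
- Further: events <70, events <54, nocturnal hypoglycemia and CV = 4.
- Total 5 + 4 = 9, if this wear is their source. That is an inference: SoC participants monitor by fingerstick, and no other follow-up blinded wear is described.

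**5. Participants who might wear two sensors**
- 30 randomized 1:1 gives 30 / 2 = about 15 in Telemedicine.

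**The case against.** The strongest defence is that the present window is matched: both arms are recorded 0 to 10 days after a scheduled visit. A window from +170 would be unmatched in that respect, at 80 to 90 days in SoC against 2 to 21 in Telemedicine, and could still open two days after a telemedicine adjustment. SoC glucose after the +180 visit is also still glucose under SoC. For the +180 remote visit the protocol specifies only laboratory work; adjustment is described for telemedicine visits in general.

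Much of this stands. Identical blinded wear in both arms is sound and should stay. But matching does not bring the window back inside the trial period. The unequal intervals before +180 follow from the visit schedules being compared, whereas changes made at the closing visits come at the end of the period under test.

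Some stronger readings are tempting, but the documents do not support them:
- **That the baseline-to-follow-up difference in timing itself biases the group comparison.** The baseline wear is described before randomization and is common to both arms, and its value is in the model. Only a difference between arms in what changes at or after +180 could bias the comparison.
- **That Day 0 adjustments cannot reach the baseline recording.** The order of the text suggests this, but no day is given and completion of the wear before Day 0 is not stated.
- **That telemedicine participants are off their intervention during the wear.** Continued device use and review are neither stated nor excluded.

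**Conclusion.** The concern holds as a fault of measurement timing. Followed as written, the plan yields six-month CGM values from about +180 to +190, almost entirely after the stated end of follow-up, after the last scheduled telemedicine contact and after any change made at the +180 visits.

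Both arms can change at +180, by different routes, so neither the size nor the direction of any bias can be derived. Up to nine secondary and further outcomes are concerned. HbA1c, obtained at +180, is not.

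The conclusion assumes that this wear is the source of the six-month CGM outcomes and that the +180 contacts take place on or close to one day. The change should be made, but it does not touch the primary analysis. Confidence is medium.

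**What to change.** Replace the research-visit text for both arms with wording to this effect:

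> A blinded CGM is placed at about +170 days, worn for ten days and collected at +180, before that day's clinic, remote or exercise contact. This wear is the source of the six-month CGM outcomes.

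The Senior Fitness test can stay at +180. The protocol should also state whether the blinded sensor is worn alongside or instead of the telemedicine participant's own CGM, and reconcile the answer with the assigned intervention. That choice belongs to the investigators. The change proposed here moves only a measurement. Giving a day for the baseline wear would settle its order relative to Day 0.

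If placement at +180 is kept, the protocol should name the wear as the outcome source, reconcile the end-of-trial label with recording to about +190, and state the order of the +180 contacts and what device use and clinician review apply during the wear.

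**Cost.** The change is to protocol wording. Placement at +170 and return at +180 replace placement at +180 and return at +190, so research contacts stay at two. Placement moves off the +180 visit day, which adds one trip if return was meant to be by mail; the protocol does not say. About 15 telemedicine participants may wear two sensors for ten days.

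### PROC GENMOD with a normal distribution, at its defaults, tests HbA1c in 30 patients at a true level of about 7.4% rather than 5% (one six-month value per patient)

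*Combined protocol and SAP*

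**What the plan says.** The STATISTICAL ANALYSIS section takes "For continuous outcome measures (e.g., HbA1c, time <54 mg/dL, etc" and so on as one class and names the tool for it: "we will use linear regression analyses (SAS proc genmod with a normal distribution and identity link". Change from baseline is modelled on the baseline value, group and time, with group and time then listed a second time (presumably an interaction). Estimates and group differences come from the "SAS LSMeans statement with a pdiff option". The decision rule is "A two-tailed $P \leq 0.05$ will indicate significance".

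On size, the Patient Population-Study Procedures section says "No sample size calculations are provided due to the pilot nature of this study" and "we used a convenience sample of 30 subjects", with patients "randomly assigned using a computer-generated random sequence at a 1:1 ratio".

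The plan gives no option for the scale estimate, no t or F reference, no REML and no other small-sample correction.

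**The concern.** A normal linear model has exact small-sample inference: estimate the residual variance with n minus p in the denominator (p being the number of mean parameters) and refer the group difference to a t distribution. The named procedure does neither by default. It fits by maximum likelihood, so the variance is divided by n, and it tests LSMeans differences against the normal distribution. Both departures make the standard error or the cutoff too small, so they push the same way. They are negligible in hundreds of patients but not in 30.

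At stake is the level of the primary HbA1c test and the width of its confidence interval. In a pilot the interval may matter more than the P-value, because it is what the next trial would be sized from.

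The point is separate from the unclear model terms. It remains in the cleanest possible analysis, with one follow-up value per patient.

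**Working it through.** **Inputs**
- Two-sided level 0.05, so z = 1.960 (STATISTICAL ANALYSIS).
- n = 30, allocated 1:1 (Patient Population-Study Procedures).
- Procedure, LSMeans comparison and model terms: STATISTICAL ANALYSIS.
- Default behaviour of the procedure (variance RSS/n, z reference): a property of the software, not stated in the documents.
- Base layout, p = 3 (intercept, baseline, group), one six-month value per patient. This fits the visit schedule: blinded CGM is recorded in both arms only at baseline and +180 days, and after Day 0 the telemedicine arm has HbA1c scheduled only at +180 days. Standard of care also has HbA1c at +90.
- Dropout: no rate stated. Completer numbers below 30 are assumptions.

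The plan's only figure to reproduce is the nominal 0.05. A t test on n − p degrees of freedom gives exactly 0.05 in the base layout under normal errors.

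**Formula.** The maximum-likelihood standard error equals the usual one times √((n − p)/n). The default rule therefore rejects when the ordinary t statistic satisfies

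`|t| > 1.960 × √((n − p)/n)`

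and its true level is the two-sided tail of t on n − p degrees of freedom beyond that cutoff.

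**Base case, n = 30, p = 3**
- √(27/30) = 0.949, so the standard error is understated by 5.1%.
- Cutoff: 1.960 × 0.949 = 1.859. Correct cutoff: 2.052 on 27 df.
- True level: P(|t| on 27 df > 1.859) = 0.0739, so coverage is 92.6%.
- Interval width ratio: 1.859/2.052 = 0.906, so the interval is 9.4% too narrow.
- A GENMOD P of 0.05 is a t-test P of 0.074. Conversely, a t-test P of 0.05 corresponds to z = 2.052/0.949 = 2.163, a GENMOD P of 0.031.

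**Other layouts and completer numbers** (same formula; multi-row cases treat rows as independent)

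| Layout | n | p | True level |
|---|---|---|---|
| One value per patient | 30 | 3 | 7.4% |
| One value, 28 complete (assumed) | 28 | 3 | 7.6% |
| One value, 24 complete (assumed) | 24 | 3 | 8.1% |
| 3-month HbA1c in standard of care only | 45 | 4 | 6.9% |
| 3 and 6 months in everyone | 60 | 5 | 6.6% |
| 75 rows | 75 | 6 | 6.4% |
| 75 rows | 75 | 5 | 6.2% |

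The 45 rows are 30 six-month values plus 15 three-month values. The 75 rows are 15 × 3 in standard of care plus 15 × 2 in telemedicine, counting baseline rows.

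**Variants at n = 30, p = 3.** The likelihood-ratio version gives 6.5%. The unbiased variance with a z reference gives 6.0%. Both exceed 5%.

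**Simulation** (20,000 trials per setting; assumed correlations 0.5 between baseline and follow-up, 0.5 to 0.7 between follow-ups). The base layout at n = 30 gave 7.4% for the default rule and 5.0% for the t test. The simulation codes the assumed default rule, so it confirms the algebra and not what the trial's program will do.

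**The case against.** The strongest reply has five parts.

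**Layout.** The written model has time terms, and a reader might infer that 7.4% is the level of the analysis exactly as written. The documents do not support that: 7.4% belongs to one six-month value per patient, and layouts closer to the written model give about 6.2% to 6.9% from the procedure alone. If baseline rows with zero change are kept, simulation gives about 12% (11.7% to 12.4%, with 90 rows). But the ordinary t test in that layout already runs at 9.9% to 10.5%, so most of the excess comes from the baseline rows and should not be charged to this procedure.

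**Outcomes.** A reader might also extend the figure to every continuous outcome. The formula needs normal errors. Time below 54 mg/dL is bounded and likely to be skewed. With assumed lognormal outcomes (40,000 trials, n = 30, with and without half zeros), the default rule rejected 5.7% and the t test 3.3% to 3.4%. Neither is exact there.

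**Dropout.** The 8.1% should not be read as the expected level. It rests on 24 completers, which is an assumption.

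**Software.** The defaults are not in the documents, and the program could override them. That is fair, and the finding is conditional on it. But the plan names the procedure and the comparison statement and says nothing to override them.

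**Pilot.** This is a pilot with a convenience sample, feasibility is part of its purpose, and other model problems may matter more. That lowers the severity. It does not remove the point, because the plan still names HbA1c as primary and sets a significance rule.

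**Conclusion.** Wrong as written; moderate severity. Under the named procedure's defaults, the HbA1c test does not have its stated 5% level. For one six-month value per patient, three parameters and roughly normal errors, the true level at n = 30 is about 7.4%, with an interval about 9% too narrow. With several visits entered as independent rows, the procedure contributes a smaller excess, to about 6.2% to 6.9%. The direction is the same in every normal-error layout checked.

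The point estimate is not biased by this. In the single-visit analysis of 30 patients, the conclusion changes only if the GENMOD P-value falls between about 0.031 and 0.05.

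The finding assumes that no scale or degrees-of-freedom override is used, and it is limited to outcomes with approximately normal errors.

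**What to change.** For continuous outcomes, replace the GENMOD specification with least-squares ANCOVA of the six-month value on baseline and group (PROC GLM), reporting t-based P-values and 95% confidence intervals for the group difference. With baseline as a covariate, the group estimate is the same whether the response is the six-month value or the change. Cost: one line in the plan and in the program. The point estimates for that model do not change; P-values and intervals become slightly less favourable.

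If more than one post-baseline visit is to be modelled, use PROC MIXED with REML, a stated within-patient covariance structure and Kenward-Roger degrees of freedom. This costs more: the covariance structure must be written down in advance, and the estimates may shift slightly because incomplete data are weighted differently. Changing to plain least squares would not deal with repeated rows per patient.

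Neither change makes the test exact for skewed outcomes such as time below 54 mg/dL. Make the change before the data are analysed, so that the choice cannot depend on which P-value results.

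### The regression uses several rows per patient with no within-patient correlation stated, so some standard errors are wrong; size and direction depend on which three-month data exist and which contrast is tested

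*Combined protocol and SAP*

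**What the plan says.** Patients are the randomised units: "Participants will be randomly assigned using a computer-generated random sequence at a 1:1 ratio" (Patient Population-Study Procedures). The same section gives the size and its basis: "we used a convenience sample of 30 subjects" and "No sample size calculations are provided due to the pilot nature of this study".

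Under STATISTICAL ANALYSIS, for continuous outcomes, "we will use linear regression analyses (SAS proc genmod with a normal distribution and identity link"); counts get Poisson regression in the same procedure. The response is change in outcome. The terms are baseline value, group and time, after which group and time are listed a second time, "where group will be control or telemedicine and time will be baseline, three-month, or six-month". Estimated values at each time point are to come from LSMeans with the pdiff option. The threshold is: "A two-tailed $P \leq 0.05$ will indicate significance". No REPEATED statement, patient identifier, random effect or covariance structure appears.

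The visit lists bear on which rows will exist. At the standard-of-care (SoC) clinic visits on days +90 and +180, "Vital signs and HbA1c will be obtained, physical examinations will be performed". For the telemedicine arm, post-baseline HbA1c is listed only at the last remote visit (+180). Blinded CGM is worn at baseline and at +180 in both arms.

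**The concern.** A time term with three levels needs more than one row per patient. Ordinary regression on such rows treats them as if they came from different patients. Two changes measured in one patient are normally correlated, so the model's standard errors are wrong in a direction that depends on the contrast. A between-arm effect pooled over visits gets a standard error that is too small; a within-patient comparison of visits gets one that is too large. At stake is whether the P-values printed by LSMeans and pdiff carry their stated 5% error in a trial of 30 patients.

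**Working it through.** **Inputs.** From the plan: 30 patients, 1:1, taken as 15 v 15; two-sided 0.05; baseline-adjusted change; time levels as above. Not in the plan, so assumed: rho, the correlation between a patient's three- and six-month changes given baseline, shown over 0.2 to 0.9. The simulations used change = -0.4 x standardised baseline + error (unit SD), no group effect and 10,000 runs per setting.

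**The plan's own figure.** The only figure to reproduce is the nominal 5%. With rho = 0, the formula in case 1 gives 5.0%; the simulated additive group test with a t reference gives 4.6%.

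**Case 1: both post-baseline visits in both arms, additive group effect, baseline rows dropped.** For residual variance s^2, the mean of a patient's two changes has variance s^2(1+rho)/2; the independent-row model assumes s^2/2. The variance ratio is 1+rho, so the actual error is 2 x (1 - Phi(1.96/sqrt(1+rho))).

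| rho | 1.96/sqrt(1+rho) | formula | simulated, t | simulated, z |
|---|---|---|---|---|
| 0 | 1.960 | 5.0% | 4.6% | 6.2% |
| 0.2 | 1.789 | 7.4% | - | - |
| 0.5 | 1.600 | 11.0% | 11.3% | 13.2% |
| 0.7 | 1.503 | 13.3% | 13.4% | 15.6% |
| 0.8 | 1.461 | 14.4% | 14.9% | 17.3% |
| 0.9 | 1.422 | 15.5% | - | - |

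The z column uses GENMOD's maximum-likelihood scale with a normal reference. Its excess over t, about 2 points, is a separate small-sample error. At rho = 0 with 60 rows and 4 parameters the z test has size 2 x P(t56 > 1.96 x sqrt(56/60)) = 6.3% with no correlation at all.

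**Case 2: HbA1c as listed** (SoC at +90 and +180, telemedicine at +180 only), baseline rows dropped. There are 15 x 2 + 15 = 45 rows in three cells. The group effect reduces to telemedicine minus SoC at six months, with one row per patient on each side, so rho barely enters. Simulated error for rho from 0 to 0.8: 5.0-5.6% (t), 6.9-7.5% (z).

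The three- versus six-month comparison reduces to a paired difference within SoC. Its true variance is 2s^2(1-rho)/15; the model uses 2s^2/15. The error is therefore 2 x (1 - Phi(1.96/sqrt(1-rho))). At rho = 0.5 this is 2 x (1 - Phi(2.772)) = 0.6%, and a simulation with a t reference also gave 0.6%.

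**Case 3: both visits in both arms, with the repeated terms read as a group-by-time interaction, baseline rows dropped.** The six-month contrast uses one row per patient: 4.8-5.6% (t), 6.4-7.2% (z) for rho from 0 to 0.8. The group effect averaged over visits remains inflated, at 10.8% (rho 0.5) to 14.3% (rho 0.8) by t.

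**After the fix.** One baseline-adjusted value per patient (the six-month value, or the mean of the two visits), with a t reference on 27 df and 20,000 runs: 4.8-5.1% for rho 0.5 to 0.8.

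The Poisson models have the same omission. Their error was not computed.

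**The case against.** The strongest reply is that the inflated rate needs two conditions together. First, three-month values must exist in both arms, and no listed outcome meets this. Second, the test must be of a group effect pooled over visits, which the plan never says it will run. Listing group and time twice adds nothing to a model, so a lost interaction symbol is a natural reading, and the plan to estimate values at each time point supports it. GENMOD can also handle correlated rows, so the text is silent on correlation and does not reject it.

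All of this stands as a limit on size. A reader might infer that the primary HbA1c P-value treats 30 patients as up to 60 independent observations and rejects a true null at two to three times the stated rate. The documents do not support that: the listed HbA1c schedule gives 45 post-baseline rows, and the between-arm test in case 2 is close to nominal by t. Nor do they support any single inflated rate, since they give no correlation.

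The reply does not remove the defect. The procedure, distribution, link and LSMeans option are all specified, and code written from that text has no patient term. The model names a three-month level for every outcome. Even on the listed visits, SoC patients contribute two HbA1c rows each, and the comparison of time points is badly miscalibrated.

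**Conclusion.** The point holds in a conditional form. As written, the analysis treats repeated rows from one patient as independent, so some of its standard errors are wrong, and the plan does not name one contrast that would be safe from this.

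- Three-month values in both arms, additive group effect: error about 7% to 16% for rho 0.2 to 0.9 (rho assumed), plus about 2 points if GENMOD's z test is used.
- Listed schedule, baseline rows dropped: the HbA1c group test is about 5-6% (t) or 6-8% (z) whatever rho is; the three- versus six-month comparison is far too conservative.
- Group-by-time fitted, baseline rows dropped: the six-month contrast is near nominal by t and about 7% by z.

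This should be corrected, but it is not evidence that the primary between-arm HbA1c test, on the listed visits, would be seriously inflated by within-patient correlation.

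**What to change.** In STATISTICAL ANALYSIS:

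1. Name the six-month between-group contrast, adjusted for baseline, as the treatment effect.
2. For outcomes with only a six-month value in both arms (HbA1c and blinded CGM as scheduled), fit one row per patient: ANCOVA with a t reference, or the corresponding count model.
3. Where three-month values are also analysed, use post-baseline rows only, with group-by-time and a within-patient covariance. Examples are PROC MIXED with REPEATED and SUBJECT=patient and Kenward-Roger degrees of freedom, or for counts GENMOD with REPEATED and a small-sample-corrected variance. Other valid repeated-measures methods would serve.
4. State whether the repeated terms mean an interaction, and reconcile the three-month model level with the telemedicine arm's visit list.

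The cost is SAP wording and a few lines of SAS, with no new data or patients. For contrasts that pool over visits, standard errors will be somewhat wider than the independent-row fit would print.
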